4.2 Primary Endpoint Definition

Change in cerebral NAD/ATP- α ratio measured by ^{31}P -magnetic resonance spectroscopy (^{31}P -MRS) in the posterior brain (encompassing the occipital, parietooccipital and posterior parts of the temporal cortex). The variables are continuous.

The ***primary analysis*** of the ***primary endpoint*** will be:

- The comparison between the dose stable (DS-group) and dose escalation group (DS-group), in cerebral NAD levels measured by ^{31}P -MRS at week 12 depending on randomization group and adjusted for ^{31}P -MRS at baseline.

The **secondary analyses** of the **primary endpoint** will be:

- The comparison of change over time from baseline to week 4, week 8 and week 12, between the DE-group, PL-group and the DS-group, in cerebral NAD levels measured by ^{31}P -MRS, depending on randomization group, time and their interaction adjusted for random individual intercept.
- The comparison between the dose stable (DS-group) and placebo group (PL-group), in cerebral NAD levels measured by ^{31}P -MRS at week 12 depending on randomization group and adjusted for ^{31}P -MRS at baseline.

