5.1.7 Secondary Analyses of the Primary Endpoint

The *secondary analyses* of the *primary endpoint* will be:

1. Analysis of covariance (ANCOVA) between the dose stable (DS-group) and placebo group group (PL-group), i.e. the regression of NAD levels measured by ^{31}P -MRS at week 12 depending on randomization group and adjusted for ^{31}P -MRS at baseline. No additional adjustments/covariates will be used. No correction for multiple testing will be performed.

The above-mentioned analysis will be performed in the same manner as the primary analysis for the primary endpoint.

2. Comparison of change over time from baseline to week 4, week 8 and week 12, between the DE-group, DS-group and the PL-group. This will be assessed using a linear mixed model (LME), i.e. NAD (^{31}P -MRS) at weeks 4, 8 and 12 depending on randomization group, time and their interaction adjusted for random individual intercept. The above-mentioned analysis will be performed using a linear mixed model (LME) comparing NAD level as a function of group with time and the interaction between group and time as independent variables. Individual subjects will be random effects.

The following formula will be used in R format:

```
NAD_level ~ Group + Visit + Group * Visit + (1 | Subject)
```

Visit will be treated as a numeric variable if there is no plateau effect. If there is a plateau effect in the data, visit will be treated as a factor.

The primary effect estimate will be the B-coefficient with confidence intervals and Cohen's d. Cohen's d will be calculated as the difference in the means between two groups and divided by the pooled standard deviation.

The dose stable group will be set as the reference to which the dose escalation and placebo groups will be compared.

No additional covariates will be included in the LME model.

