5.3 Methods for Continuous Exploratory Endpoints

As described in section 4.4, due to the nature of the exploratory outcomes, the analysis method is subject to change. The preliminary plan is that they will be analysed in the same manner as the primary endpoint if they have observations at V1, V2, V3 and V4 (see sections 5.1.2 and 5.1.7) and the same manner as the secondary endpoint if they only have observations at V1 and V4 (see sections 5.2.2 and 5.2.7).

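### An undefined plateau rule decides whether Visit is a line or a factor in the only group comparison of cerebral NAD at weeks 4 and 8; a retained line cannot separate the dose steps

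*SAP*

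**What the plan says.** SAP 5.1.7, item 2, fits a linear mixed model with Group, Visit, their interaction and a random intercept per patient. Two sentences set the form of Visit: "Visit will be treated as a numeric variable if there is no plateau effect" and "If there is a plateau effect in the data, visit will be treated as a factor". Protocol 10.4 describes the same kind of model for DE and DS only, without this switch.

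The text points two ways on which rows enter. SAP 5.1.7 models NAD "at weeks 4, 8 and 12 depending on randomization group, time and their interaction adjusted for random individual intercept", which suggests three post-baseline rows. SAP 4.2 describes "The comparison of change over time from baseline to week 4, week 8 and week 12, between the DE-group, PL-group and the DS-group", and SAP 5.3 says that exploratory outcomes will be "analysed in the same manner as the primary endpoint if they have observations at V1, V2, V3 and V4"; both lean towards including V1 without settling it.

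On reporting: "The primary effect estimate will be the B-coefficient with confidence intervals and Cohen's d". The reference is fixed: "The dose stable group will be set as the reference to which the dose escalation and placebo groups will be compared". The absence of a baseline term is also fixed: "No additional covariates will be included in the LME model".

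The model serves the first secondary objective (SAP 1.3.2), the dose-response of cerebral NAD over 1000, 2000 and 3000 mg at weeks 4, 8 and 12. Both ANCOVAs of cerebral NAD (SAP 5.1.2 and 5.1.7 item 1) use week 12 only, and SAP 5.1.1 is descriptive. This model is therefore the only specified group comparison at weeks 4 and 8.

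**The concern.** The model form is to be picked after looking at the data, by a criterion that nobody could apply twice and be sure of the same answer. The SAP does not say whether the plateau is sought over time at constant dose (DS) or over dose (DE), by what test or threshold, or whether the judgement is made blinded.

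The choice changes what is estimated. DE takes 1000, 2000 and 3000 mg in successive months, so week 8 is its only reading at 2000 mg. A line in Visit reduces the DE-DS comparison to one slope and makes the two dose steps equal by construction. A response that stops rising at 2000 mg would then be reported as still rising at 3000 mg. SAP 5.3 carries the same method, as a preliminary plan, to exploratory outcomes measured at all four visits.

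**Working it through.** The plan gives no figure for this model, so there is none to reproduce. The check fits least-squares lines to the mean profiles that the plan implies. With complete data, these equal the expected fit of the random-intercept model.

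**Inputs**
- Effect of 1000 mg: a factor of 1.27 on baseline (SAP 5.5), so +27% of baseline.
- Linear in dose (SAP 5.5): +27 per 1000 mg, giving 27, 54 and 81.
- Assumption: at constant dose, NAD is flat from week 4. The footnote in protocol 10.3 reports a plateau within 1-2 weeks, but in healthy people and people with Parkinson's disease, and does not say that this was cerebral NAD.
- Hypothetical alternative: response levels off at 2000 mg.

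**Mean profiles at V1/V2/V3/V4**
- DS: 0/27/27/27
- DE, linear in dose: 0/27/54/81
- DE, levelling off: 0/27/54/54

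**Lines through V1-V4.** Centred visits are -1.5, -0.5, 0.5, 1.5, with sum of squares 5.
- DS: slope = (-0.5×27 + 0.5×27 + 1.5×27)/5 = 40.5/5 = 8.1; fitted 8.1/16.2/24.3/32.4.
- DE linear: slope 27; fitted 0/27/54/81.
- DE levelling off: slope = (-13.5 + 27 + 81)/5 = 18.9; fitted 5.4/24.3/43.2/62.1.

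**Lines through V2-V4.** Centred visits are -1, 0, 1, with sum of squares 2.
- DS: 27/27/27.
- DE linear: 27/54/81.
- DE levelling off: slope = (54 - 27)/2 = 13.5; fitted 31.5/45/58.5.

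**DE minus DS, % of baseline**

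| Case | Fitted, weeks 4/8/12 | True | Fitted 2000-to-3000 mg step | True step |
|---|---|---|---|---|
| V1 in, linear | 10.8/29.7/48.6 | 0/27/54 | 18.9 | 27 |
| V1 in, levelling off | 8.1/18.9/29.7 | 0/27/27 | 10.8 | 0 |
| V1 out, linear | 0/27/54 | 0/27/54 | 27 | 27 |
| V1 out, levelling off | 4.5/18/31.5 | 0/27/27 | 13.5 | 0 |

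In the first row the week-4 difference is spurious, because both arms take 1000 mg until then. With Visit as a factor, all four cases are exact in expectation.

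**How often would the line be kept?** This depends on a test and an SD that are not stated. Take V1 out, levelling off, 40/20 completers and an assumed residual SD of 24.5.
- A 5% test of linearity within DE: departures from the line are -4.5/9/-4.5, sum of squares 121.5; noncentrality 40×121.5/24.5² = 8.1; z = 2.85. The flattening is found in about 81% of trials.
- A 5% test of unequal DE-DS steps: SE = 24.5×√(6×(1/40+1/20)) = 16.4; z = 27/16.4 = 1.64. It is found in about 38%.

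The same truth gives two very different chances of keeping the line.

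**Precision of the 2000-to-3000 mg step,** in residual SDs, 40/20 completers, where 1/40+1/20 = 0.075
- Factor: √(2×0.075) = 0.39
- V2-V4 line: √(0.075/2) = 0.19
- V1-V4 line: √(0.075/5) = 0.12

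**The case against.** The strongest reply is that each case with an error contains a flattening, which is what the switch is there to catch. With an assumed residual SD of 20 and a 5% linearity test within the arm that flattens, the factor would be chosen in about 85% of trials (V1 in, linear; tested in DS), 99% (V1 in, levelling off; DE) and 94% (V1 out, levelling off; DE). With a residual SD of 24.5 the figures are 67%, 94% and 81%. On the authors' own expectation in protocol 10.3, DS would be flat by week 4, which may itself trigger the factor if V1 rows are in. This stands as a limit on size: the tabulated errors are not an expected bias. It does not rescue the rule, because that test is supplied by the reader and another reasonable one catches far less.

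A reader might infer that the reported coefficient is wholly unidentified. It is not. With numeric Visit, the stated aim of comparing change between groups and the DS reference point to the Group-by-Visit slopes. Only the factor branch leaves the visit open.

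A reader might also fault the missing baseline covariate. The SAP settles that explicitly. With V1 rows out, the omission costs precision but does not bias a randomised comparison.

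Finally, the objective asks for a dose-response relationship, not for a separate 2000-to-3000 mg contrast, and under the plan's linear assumption a slope is a legitimate summary. That is fair, but a line cannot show whether the assumption holds.

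**Conclusion.** The point holds in conditional form. The SAP leaves the form of Visit to an undefined, data-judged plateau and does not settle the role of V1, in the only specified group comparison of cerebral NAD at weeks 4 and 8. If the line is kept, the dose steps cannot be separated. Under the assumptions above, the error reaches 10.8 points of baseline at week 4 in the plan's own linear scenario. In the hypothetical levelling-off scenario, a true zero step reads as 10.8 or 13.5 points. If the factor is selected, or if V1 is out and response is linear in dose, there is no such error.

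Two stronger readings are not supported. The documents do not show that this analysis will be biased, because how often the line would be kept cannot be determined from them. Nor do they show any damage to the primary result: the DE-DS and DS-PL week-12 ANCOVAs do not use Visit. This is a secondary analysis that should be tightened.

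**What to change.** - Delete the plateau switch in SAP 5.1.7 and pre-specify Visit as a factor, for example `NAD_level ~ Group * factor(Visit) + (1 | Subject)`.
- State whether V1 is an outcome row or a baseline covariate. Either is acceptable. The covariate form means amending the sentence that rules out further covariates, and it drops patients without a V1 scan.
- Replace the unnamed coefficient with DE-DS contrasts at weeks 4, 8 and 12 and the change in DE-DS from week 8 to week 12, each with a 95% confidence interval. Keep placebo against DS as the SAP already has it.
- Align the mixed-model wording in protocol 10.4, which names only DE and DS.

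The cost is wording, a few lines of R and a few more parameters. The interval for the 2000-to-3000 mg step widens: its SE is about 0.39 residual SDs with 40/20 completers, against 0.19 for a V2-V4 line or 0.12 for a V1-V4 line. The lines are tighter because they force the two steps to be equal.

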Fig 1. Results of the NR-SAFE trial. A: Metabolomics were performed in snap-frozen blood from the NR-SAFE participants at baseline (V2) and after 30 days of treatment (V9). Oral NR intake at a dose of 3000 mg daily induced a potent (up to 5-fold) and highly significant augmentation of NAD+ and NADP+ levels, as well as a clear increase of the redox ratio (NAD+/NADH) and the NADP+/NADPH ratio. P-values indicate the results of paired t-tests in the NR-group. There were no significant changes in the placebo group. B: Oral NR intake at a dose of 3000 mg daily was associated with a significant and substantial decrease in total MDS-UPDRS in the NR (mean decrease  $14 \pm 13.7$ ; paired t-test: p = 0.01), but not in the placebo (mean decrease  $1 \pm 12.7$ ; paired t-test: p = 0.81). C: At the group level, the change (delta) in total MDS-UPDRS in the NR group was significantly (t-test, P = 0.02) larger than that of the placebo group (B).

**Key:** V2: baseline; V9: after 30 days of treatment; NR: the group receiving NR 3000 mg daily; PL: the placebo group.

The results from our phase I trials suggest that NR holds promise as a neuroprotective therapy against neurodegenerative diseases. These results must now be replicated in AD. Several essential knowledge gaps (KG) must now be addressed in order to further develop NR towards an AD-drug, so that we may harness its full therapeutic potential and maximize clinical benefit and impact.

**KG1 – What is the Optimal Biological Dose (OBD) of NR in AD?** We define the OBD of NR as the dose required to achieve an optimal neurometabolic response in AD, i.e., maximal cerebral NAD increase or optimal change in cerebral metabolic pattern, in the absence of toxicity.

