# 1.4 Rationale for the Study and Purpose

Our phase I trial (NADPARK) showed that NR holds great promise as a potential neuroprotective, disease-modifying therapy for neurodegenerative diseases. Encouraged by these findings, this project aims to determine the optimal biological dose of NR in AD and to further explore its neuroprotective potential. We propose that oral administration of the NAD precursor NR (Niagen\*, Chromadex) in increasing dosages up to 3000 mg will show a dose-responsive improvement in the cerebral metabolism in AD patients and show signs of improved mitochondrial function, histone acetylation, neuroinflammation and clinical symptoms.

The outcomes of this project will take us several steps closer to developing NR into an AD-drug, so that we may harness its full therapeutic potential and maximize its clinical benefit and impact.

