1.3.2 Secondary Objectives

The secondary objectives of this study are to:

- Assess the dose-response relationship between NR dose (1000 mg, 2000 mg, 3000 mg per day) and changes in cerebral NAD levels from baseline to weeks 4, 8 and 12.

- Compare the effectiveness of orally administered nicotinamide riboside (NR) 1500 mg twice per day versus 500 mg twice per day in augmenting the NAD-metabolome in the central nervous system (CNS) at week 12.

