5.1.2 Primary Inferential Analysis

The ***primary analysis*** of the ***primary endpoint*** will be performed using analysis of covariance (ANCOVA) between the dose stable (DS-group) and dose escalation group (DE-group), i.e. the regression of NAD levels measured by ^{31}P -MRS at week 12 depending on randomization group and adjusted for ^{31}P -MRS at baseline. No additional adjustments/covariates will be used. As this is the single primary outcome, alpha will be set at 0.05. No correction for multiple testing will be performed.

The formula for this calculation in R is:

```
lm_object = lm(NAD_at_V4 ~ Group + NAD_at_V1)
```

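### No pre-specified analysis shows whether 3000 mg adds to 2000 mg: the mixed model defaults to a numeric visit, and the 3000 v 2000 mg contrast is never named

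*SAP*

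**What the plan says.** Protocol 1.4 states that "this project aims to determine the optimal biological dose of NR in AD and to further explore its neuroprotective potential". Protocol 1.1.3, under KG1, gives the definition: "We define the OBD of NR as the dose required to achieve an optimal neurometabolic response in AD", which it explains as the largest cerebral NAD increase or the best change in metabolic pattern, without toxicity. Among the formal objectives, SAP 1.3.2 lists: "Assess the dose-response relationship between NR dose (1000 mg, 2000 mg, 3000 mg per day) and changes in cerebral NAD levels".

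Two inferential analyses compare the dose-escalation (DE) and dose-stable (DS) groups on cerebral NAD:

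- **Primary (SAP 5.1.2).** ANCOVA of week-12 NAD on group and baseline, DE v DS. At week 12 this is 3000 v 1000 mg.
- **Secondary (SAP 5.1.7, item 2).** A mixed model with group, visit, their interaction and a random subject intercept. Dose is not a term. "The dose stable group will be set as the reference to which the dose escalation and placebo groups will be compared". Visit is numeric if there is no plateau; otherwise, "If there is a plateau effect in the data, visit will be treated as a factor". No criterion for a plateau is given.

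The SAP does not mention the OBD.

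**The concern.** In DE, dose rises with visit: 1000 mg to V2, 2000 mg to V3, 3000 mg to V4. A dose-response claim over three doses, and any statement on the OBD, needs to know what happens between V3 and V4 in DE, net of any change over the same weeks in DS.

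The primary test does not look at that interval. The mixed model looks at it only if visit is a factor, and then only if someone forms the difference between two interaction terms. Whether visit is a factor depends on seeing a plateau, so the feature to be tested decides the form of the model.

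The trigger is also ambiguous. The footnote in Protocol 10.3 says that NAD levels off within 1 to 2 weeks of treatment. DS should then be flat after V2 whatever the higher doses do in DE. The clause does not say whether a plateau over time in DS or a plateau over dose in DE is meant.

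At stake is the dose-response conclusion, not the validity of the primary test.

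**Working it through.** **Inputs.**
- 1000 mg multiplies NAD by 1.27, and the rise is assumed linear in dose (Protocol 10.1, SAP 5.5). With baseline set to 1, each step is 0.27.
- 20 DS and 40 DE (SAP 1.2.1); two-sided alpha 0.05 (SAP 2.3.2).
- SD: not stated, so assumed. Protocol 1.1.3 gives a paired P of 0.016 for the pilot NAD rise. SD of change = 0.27 × √n / t. With n = 13 (the number in the individual-response account in Protocol 1.1.3), t = 2.801 and SD = 0.347. With n = 15 (Protocol 10.1), t = 2.739 and SD = 0.382.

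**The plan's own figure.** The 30 in DE for 90% power cannot be reproduced, because no SD, test or contrast is given. If it refers to DE v DS at week 12 (difference 0.54) with 2:1 allocation, the implied SD is 0.54 / [(1.960 + 1.282) × √(1/15 + 1/30)] = 0.53. I use this as the upper case.

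**Two shapes.** DS is 1, 1.27, 1.27, 1.27 in both.

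| Shape | DE at V1, V2, V3, V4 | DE − DS at V3 | DE − DS at V4 |
|---|---|---|---|
| Continuing rise | 1, 1.27, 1.54, 1.81 | 0.27 | 0.54 |
| Plateau at 2000 mg | 1, 1.27, 1.54, 1.54 | 0.27 | 0.27 |

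**Primary ANCOVA under the plateau.** Simulation used 2000 trials per case, 20 v 40, compound symmetry, and within-subject correlation ρ of 0.3 to 0.7. The share of positive trials was 0.85–0.92 (SD 0.35), 0.80–0.89 (SD 0.38) and 0.49–0.63 (SD 0.53). A rerun with another seed agreed within about 3 points, so I write about 80 to 93%, and about 50 to 63% at SD 0.53. Hand check at SD 0.35, ρ = 0.5: residual SD = 0.35 × √((1 + 0.5)/2) = 0.303; SE = 0.303 × √(1/20 + 1/40) = 0.083; 0.27/0.083 = 3.25; Φ(3.25 − 2.00) = 0.89. Under the continuing rise, 0.98–1.00 are positive.

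**Numeric visit.** The interaction estimates one slope difference. Over V1–V4, with visits centred at −1.5, −0.5, 0.5, 1.5 (sum of squares 5):
- rise: (0.5 × 0.27 + 1.5 × 0.54)/5 = 0.189 per visit;
- plateau: (0.5 × 0.27 + 1.5 × 0.27)/5 = 0.108 per visit.

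The SAP text can also be read as modelling weeks 4 to 12 only; the values are then 0.270 and 0.135. Both shapes give a positive slope. A slope of 0.108 equally fits a continuing rise with steps of 0.27 × 0.108/0.189 = 0.154. In simulation (t-test on per-subject slopes, V1–V4) the slope difference was significant in about 0.90–0.95 of plateau trials at SD 0.35–0.38 and about 0.63–0.65 at SD 0.53.

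**The unnamed contrast.** 3000 v 2000 mg = (DE V4 − V3) − (DS V4 − V3). Its expectation is 0.27 under the rise and 0 under the plateau, where it rejected in 4–6% of trials. Assuming the V3-to-V4 change has the same SD as the pilot change, SE = SD × √(1/20 + 1/40), with t(58) = 2.002 and power from the noncentral t for a step of 0.27:

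| SD | SE | 95% CI half-width | Power |
|---|---|---|---|
| 0.347 | 0.095 | 0.19 | 0.80 |
| 0.382 | 0.105 | 0.21 | 0.72 |
| 0.53 | 0.145 | 0.29 | 0.45 |

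The 40 already contains a margin over 30. With 30 v 15 completers at SD 0.347, SE = 0.347 × √(1/15 + 1/30) = 0.110, the half-width is 0.22 and power is 0.67.

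**The case against.** Four points can be made for the plan.

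1. **The contrast is available.** With visit as a factor, the DE-by-V4 minus DE-by-V3 interaction difference is exactly 3000 v 2000 mg net of DS. This stands. A reader might infer that the model cannot give the contrast, or that the DS reference blocks it. Neither is so: DS is the right reference, and the obstacles are the numeric default and the missing specification.

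2. **Rejecting the primary null under a plateau is no error.** The null in SAP 2.3.1 is that the increase is not dose-responsive. A rise up to 2000 mg makes that false. This stands. One might also infer that a positive result would select the top dose, or that the trial cannot answer its own title. No passage says the first, and the data for the comparison are collected, so the second does not follow.

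3. **Other material bears on the step.** Protocol 10.5 mentions mean change between and within arms, SAP 5.1.1 tabulates NAD by group and visit, and SAP 6.1.1 tabulates adverse events by dose level. But the first names no visit or dose pair, and the tables supply no interval for the step.

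4. **The OBD aim is in the introduction and rationale, not the objectives table.** True, but the three-dose secondary objective is formal, and it needs the 2000 v 3000 mg comparison.

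**Conclusion.** The concern holds as a gap in specification with a real consequence. A positive primary test is likely under either shape, so it does not show that 3000 mg adds to 2000 mg. Neither does a significant numeric-visit interaction. The one contrast that separates the shapes is left to a data-driven switch and an unstated calculation, and nothing says how results would become an OBD statement.

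The structural point needs no assumption about variance. The sizes do: they rest on an SD the plan does not give, the plan's own step of 0.27, complete data unless stated, and compound symmetry. Reading the contrast as a dose effect also assumes that DS carries the same time trend as DE. This should be changed, but the primary analysis remains valid without it.

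**What to change.** In SAP 5.1.7, item 2:

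- Treat visit as a factor in all cases and delete the plateau switch. Without this, the contrasts below cannot be estimated.
- Pre-specify, with 95% CIs, 3000 v 2000 mg = (DE V4 − V3) − (DS V4 − V3), alongside 2000 v 1000 mg = (DE V3 − V2) − (DS V3 − V2). The second is close to the week-8 DE v DS comparison, since both arms take 1000 mg up to V2, but stating both shows each step.
- State that the primary test alone shows only that 3000 differs from 1000 mg, and that any OBD statement rests on these contrasts together with the adverse-event tables.

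The cost is a few lines in the SAP, fixed before unblinding. 31P-MRS is already scheduled at all four visits, and the primary analysis does not change.

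The downside should be written in too. With a half-width of about 0.19 to 0.29 against an assumed step of 0.27, a non-significant last-step contrast does not prove a plateau. The sponsor must accept that the OBD may be reported as not determined.
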